#### 1.5 Rationale

Optimizing immune checkpoint blockade will be possible with the conduct of trials utilizing combination-targeted therapies. One such target is MEK. Balko and colleagues {Balko 2014} evaluated genomic alterations in tumors that may be associated TILs in residual tumor after NAC in TNBC. In parallel to previous studies, increased TILs are associated with favorable outcomes, including DFS ( $p = 0.0008$ ) and OS ( $p = 0.007$ ). There appeared to be a trend toward reduction in TIL level among patients who did not achieve pCR ( $p = 0.07$ ). Using next-generation sequencing, lower TIL level in residual disease after NAC was associated with genetic alteration in the Ras/MAPK pathways, including KRAS, BRAF and RAF1 amplifications and NF1 truncations ( $p = 0.005$ ). There was also an inverse correlation between the MEK activation signature and TILs in residual disease samples ( $p = 0.00028$ ). These findings suggested that the association between TIL levels and dysregulation of Ras/MAPK pathway may be pathway specific.

The investigators further evaluate the effects of MEK inhibition in several TNBC cell lines and found that MEK inhibition, using AZD6244, up-regulates major histocompatibility complex (MHC) class I and II molecules in both *in vitro* and *in vivo* models. The investigators also went back and evaluated the expression of HLA-A and HLA-DR in their patient samples and found the inverse correlation between the expression level of these MHC class I and II molecules and the MEK activation signature. However, there was also a significant increase in the PD-L1 expression after MEK inhibition treatment, which has opposing inhibitory effects on tumor immune surveillance. The investigators further investigated the combination of MEK inhibitor and anti-PD-L1 antibody in *in vivo* mouse model and found that the combination can completely eradicate the tumors, while each single agent only had modest effects on tumor growth.

Currently, there is no clinical trial evaluating the combination of pembrolizumab and binimetinib in breast cancer. Based on the intriguing preclinical data above, it is logical to develop and conduct a phase I/II trial of pembrolizumab in combination with binimetinib in patients with unresectable locally advanced or metastatic triple negative breast cancer.

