#### 1.61 Correlative studies for tumor tissue

We will perform the following correlative studies using tumor tissue.

1. Tumor infiltrating lymphocytes: Tumor infiltrating lymphocytes will be quantified based on the H&E as described (2). Furthermore, the composition of different subsets of lymphocytes will also be quantify using immunohistochemistry staining for CD4 for T helper cells, CD8 for cytotoxic T cells as well as CD25 and FOXP3 for regulatory T cells as we previously published (3).
2. PD-L1 expression: PD-L1 expression in the tumor will be assessed by immunohistochemistry as previously described {Topalian, 2012}

3. Gene expression analysis: Global assessment of immune-related gene expression in pre- and post-treatment tumors will be assessed using the NanoString PanCancer Immune Profiling Panel which includes 770 genes for 24 different immune cell types and populations, 30 common cancer antigens and genes that represent all categories of immune response including key checkpoint blockade genes.
4. PDJ amplification: We have recently reported that approximately 30% of patients with TNBC harbor PDJ amplification (4). Locating at chromosome 9p24.1, this amplicon encompasses JAK2, PD-L1, and PD-L2 genes. TNBC patients with PDJ amplification had worse disease free (25.0% vs. 66.0%, p = 0.005) and overall survival (25.0% vs. 69.0%, p = 0.004). This amplicon has been previously described in the majority of Hodgkin's lymphoma, which has been reported to have remarkable response to Nivolumab (86% clinical benefit rate in heavily pretreated patients)(5). Based on these intriguing results, we plan to correlate PDJ amplification measured by fluorescent in situ hybridization and clinical outcome of patients in this trial.

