**2.3 Correlative Research**

2.31 To assess the correlation between ORR, PFS, or OS and baseline and/or change in TILs.

2.32 To assess the correlation between ORR, PFS, or OS and baseline and/or change in immune related gene signature and PDJ amplification.

2.33 To assess the change in immunoregulatory cells (IRC).

2.34 To assess the change in the cytokine profile.

2.35 To assess the change in circulating tumor cells (CTC).

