### 16.3 Statistical Analysis Plan

The objective of the phase I portion of the study is to estimate the maximum tolerated dose (MTD) using the standard 3+3 design. Safety/adverse events data will be tabulated, including adverse events of all grades.

For the phase II portion of the study, the overall response rate by RECIST will be estimated using the approach of Jung and Kim [On the estimation of the binomial probability in multistage clinical trials. Stat Med 23:881-96, 2004]. The 90% lower confidence bound will be calculated using the approach of Koyama and Chen [Proper inference from Simon's two-stage designs. Stat Med 27:3145-54, 2008]. Secondary efficacy endpoints include objective response rate by immune-related response criteria (irRECIST), progression-free survival (PFS) and overall survival (OS). Objective response rate by irRECIST will be estimated as a binomial proportion with a 2-sided 95% CI. PFS will be defined as the time from study enrollment to date of progression. Patients who have not progressed (including those lost to follow-up) at the time of data analysis will be censored at the date last known to be free of progression. OS will be defined as the time from study enrollment to death attributable to any cause (i.e. death from breast cancer, non-breast cancer cause, or from unknown cause). Patients who are alive (including those lost to follow-up) at the time of data analysis will be censored at the last known alive date. A Kaplan-Meier curve will be used to summarize the PFS and OS experience of this patient cohort.

Baseline TILs and percent change in TILs from baseline will be summarized. Logistic regression models will be used to assess the correlation between these biomarkers and ORR in order to assess their prognostic significance. Cox Proportional Hazard models will be used to assess their correlation with time-to-event endpoints such as PFS and OS. Similar analyses will be performed for other exploratory biomarkers such as immune related gene signature, PDJ amplification, etc. These analyses will be exploratory in nature. As such, no adjustment for multiple comparisons will be made; all hypothesis tests will be based on 2-sided alpha = 0.05 level.

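### Section 16.3 measures TIL change only as percent change from baseline, which is undefined at a zero baseline and lets low-baseline patients dominate small exploratory models.

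*Combined protocol and SAP*

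**What the plan says.** Section 16.3 defines the TIL measures in one sentence: "Baseline TILs and percent change in TILs from baseline will be summarized". It then gives their use: "Logistic regression models will be used to assess the correlation between these biomarkers and ORR in order to assess their prognostic significance", and "Cox Proportional Hazard models will be used to assess their correlation with time-to-event endpoints such as PFS and OS". It does not say whether baseline and percent change enter together or in separate models. It gives no rule for a zero or near-zero baseline, and no second change scale. It extends the same kind of analysis to other exploratory biomarkers, such as the immune gene signature.

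The status is clear: "These analyses will be exploratory in nature". There is no multiplicity adjustment, and "all hypothesis tests will be based on 2-sided alpha = 0.05 level".

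The goal behind this, 2.31 in Section 2.3, fixes no scale: "To assess the correlation between ORR, PFS, or OS and baseline and/or change in TILs". Percent change therefore comes from Section 16.3 alone.

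Sections 1.61 and 17.41 describe the measurement: H&E scoring of stromal and intraepithelial TILs, plus staining for CD4, CD8, CD25 and FOXP3. Neither states a unit, a floor or a limit of detection. Under Section 17.1 the baseline tissue is mandatory, and the samples at the end of Cycle 1 and at the end of treatment are optional.

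**The concern.** Percent change divides by the baseline. That fails at a baseline of zero and is unstable just above it, where a small absolute difference, or plain reading error, becomes a very large covariate value. Percent change is also tied to baseline through its denominator. Without baseline in the model, an association with response may reflect where a patient started rather than how far TILs moved, and Section 16.3 states no such adjustment.

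Low TIL values have some scientific interest here. Section 1.5 reports of earlier neoadjuvant samples: "There was also an inverse correlation between the MEK activation signature and TILs in residual disease samples". The measure is thus least reliable in a range that the background discusses.

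At stake is the readability of the change-in-TIL results. One low-baseline patient could produce or hide an association, and a rule for zeros chosen after seeing the data would add flexibility to unadjusted tests at 0.05.

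**Working it through.** **1. The plan's own powered figure.** The only powered analysis is the two-stage ORR design in Section 16.112: stop at 1 or fewer responses in 9, promising at more than 5 in 23, with rates 15% and 35%.

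- Early stopping at 15%: 0.85^9 + 9 × 0.15 × 0.85^8 = 0.599 (stated 60%).
- Type I error: the sum over x ≥ 2 of P(x of 9) × P(at least 6 − x of 14), at 15%, is 0.099 (stated limit 10%).
- Power: the same sum at 35% is 0.804 (stated 80%).

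The design reproduces, and the TIL scale does not enter it. No sample size or power is stated for TILs.

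**2. Behaviour of the scale.** Let B be baseline and F follow-up. Percent change = 100 × (F − B)/B; absolute change = F − B; log ratio = log2((F + 1)/(B + 1)). The baselines, the 10-point rise and the offset of 1 are illustrative, on an assumed scale that can reach zero.

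| B | F | Percent change | Absolute change | Log ratio |
|---|---|---|---|---|
| 0 | 10 | undefined | 10 | 3.46 |
| 1 | 11 | 1000% | 10 | 2.58 |
| 2 | 12 | 500% | 10 | 2.12 |
| 5 | 15 | 200% | 10 | 1.42 |
| 10 | 20 | 100% | 10 | 0.93 |
| 20 | 30 | 50% | 10 | 0.56 |
| 40 | 50 | 25% | 10 | 0.31 |

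**3. Reading error.** If nothing truly changes but two readings differ by 5 points (assumed), percent change is 500/B: 500% at baseline 1, 100% at 5, 25% at 20 and 12.5% at 40.

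**4. Influence in a small set.** Take 12 assumed pairs with baselines 1, 2, 5, 5, 10, 10, 15, 20, 20, 30, 40 and 60, each rising 10 points. Mean percent change is 195%; the median is (100 + 66.7)/2 = 83%. In a linear model with intercept and percent change, leverage is 1/n + (x − mean)²/Sxx. For the baseline-1 patient it is 0.80, against an average of 2/12 = 0.17. Leverage in a logistic or Cox fit also depends on the fitted model, so 0.80 is an indication only.

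**5. Undefined values.** The documents give no share of zero baselines. For an assumed share q among n pairs, the chance of at least one undefined value is 1 − (1 − q)^n:

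| q | n = 12 (assumed) | n = 23 |
|---|---|---|
| 2% | 22% | 37% |
| 5% | 46% | 69% |
| 10% | 72% | 91% |
| 20% | 93% | 99% |

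This shows only that modest shares would be enough to need a rule.

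**6. Information available.** At the design rates, 23 patients give 23 × 0.15 = 3.5 to 23 × 0.35 = 8.1 responders, so about 3 to 8, and fewer among those with paired tissue.

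**The case against.** A reader might infer that the plan loses the TIL-poor patients whom the rationale targets. The documents do not support that.

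- Only an exact zero is lost, and only where percent change is used. Section 16.3 also names baseline TILs, so that patient remains in the baseline summary and can enter the baseline models. Low non-zero patients are kept; their problem is undue influence.
- Section 1.5 does not say that MEK inhibition raises TILs. It reports higher MHC expression and higher PD-L1. Section 1.6 attributes increased TILs to checkpoint blockade. The TIL association comes from residual disease after neoadjuvant chemotherapy, and the eligibility criteria in Section 3 do not select on TIL level.
- A reader might also apply a guessed zero share of 5–20% to 23 patients and conclude that 1 to 5 are lost. That share is not in the documents. Nor is 23 the right denominator: Section 16.3 does not restrict the biomarker models to the ORR set, total enrolment may reach 38 (Section 16.2), and change needs an optional second biopsy. Missing biopsies may remove more patients than zero baselines do.

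Three further objections carry weight. The scoring method is in a cited source and may deal with zeros. Absolute change is not neutral: it scores 1 to 5 as 4 points and 30 to 50 as 20, where percent change gives 400% and 67%; the documents do not settle which matters biologically. And a second covariate strains a logistic model with few responders. These limit the size of the point and shape the fix. They do not rescue percent change as the sole scale: being exploratory does not make an undefined or high-leverage covariate usable.

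**Conclusion.** The point holds as a limited one. As written, Section 16.3 makes the change covariate undefined at a zero baseline, unstable just above it and tied to baseline, with no handling rule and no stated baseline adjustment. The mechanism is arithmetic; that zero or near-zero scores will occur is an assumption, since no unit or floor is given. The number of patients affected cannot be estimated from the documents.

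The reach is exploratory goal 2.31 and, because Section 16.3 extends the approach, possibly other biomarkers analysed as change. No primary or secondary endpoint depends on it. It is a minor improvement, worth making because it is cheap.

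**What to change.** In Section 16.3:

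- Replace percent change with absolute change in TILs, fitted with baseline TILs as a covariate in the logistic and Cox models.
- Add a log ratio with a fixed, stated offset as a sensitivity analysis. This keeps a relative view and is defined at zero.
- State the TIL unit, and report the number of paired samples behind each change analysis.
- Apply the same rule to any other biomarker analysed as change.

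Goal 2.31 needs no rewording, and no extra data are collected. The cost is one more covariate in a logistic model with about 3 to 8 responders among 23 at the design rates, and fewer among paired samples. Unadjusted estimates should therefore stand beside the adjusted ones, and both should be read as descriptive.

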### 16.4 Phase I

This portion of the study is designed to determine the MTD and toxicity profile of binimetinib in combination pembrolizumab.

16.41 MTD Definition: MTD is defined as the dose level below the lowest dose that induces dose-limiting toxicity (DLT) in at least one-third of patients (at least 2 of a maximum of 6 new patients). A total of 6 patients treated at the MTD will be sufficient to identify common toxicities at the MTD.

Refer to Section 7.52 for definition of dose-limiting toxicity (DLT). The focus of this study is to establish the DLT of the combination of binimetinib and pembrolizumab. Therefore, only adverse events that occur during the first cycle of treatment with the combination (Cycle 2) will be considered when evaluating for dose-limiting toxicity.

16.42 MTD Determination

The phase I portion of this study will utilize a standard cohort of three design. The dose levels to which patients will be assigned in sequential cohorts are described in Section 7.51. The first cohort of three patients will be treated at dose level 0. Decisions on when and how to dose escalate are described below.

16.421 Three patients will be treated at a given dose level combination and observed for one cycle of the combination (Cycle 2) from start of treatment to assess toxicity.

16.422 If DLT is not seen in any of the 3 patients, 3 new patients will be accrued and treated at the next higher dose level. If DLT is seen in 2 or 3 of 3 patients treated at a given dose level, then the next 3 patients will be treated at the next lower dose level, if only 3 patients were enrolled and treated at this lower dose level.

16.423 If DLT is seen in 1 of 3 patients treated at a given dose level, up to 3 additional patients will be enrolled and treated at the same dose level. If DLT is seen in at least one of these additional three patients ( $\geq 2$  of 6), the MTD will have been exceeded and further accrual will cease to this cohort. If dose-limiting toxicity (DLT) is not seen in any of the three additional patients, 3 new patients will be accrued and treated at the next higher dose level.

16.424 After enrolling 6 patients on a specific dose level, if DLT is observed in at least 2 of 6 patients, then the MTD will have been exceeded and defined as the previous dose unless only 3 patients were treated at the lower dose level. In that case, 3 additional patients will be treated at this lower dose level such that a total of 6 patients are treated at the MTD to more fully assess the toxicities associated with the MTD.

16.426 If a patient fails to complete the first combined cycle (Cycle 2) of therapy for reasons other than dose-limiting toxicity defined adverse events, the patient will be regarded as uninformative in regard to the primary study goal (i.e. MTD determination) and will be replaced.

16.427 Operating Characteristics for standard cohort of 3 design: The following table gives the probability of dose escalation at a single dose level as a function of the true probability of DLT at that level using the cohorts of 3 design described above.

True Rate of DLT (%)	Probability of Dose Escalation
10	0.91
20	0.71
30	0.49
40	0.31
50	0.17

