## 7.4 Phase I – determination of Maximum Tolerated Dose (MTD)

## 7.41 Dose De-Escalation

Dose level	Pembrolizumab**	Binimetinib
-2	200 mg IV q3w	15 mg PO twice daily
-1	200 mg IV q3w	30 mg PO twice daily
0*	200 mg IV q3w	45 mg PO twice daily

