**\*starting dose level**

\*\*NOTE: There are no dose modifications for pembrolizumab

If dose level -1 does not meet MTD determination, the study will be stopped and evaluated by the principal investigator and the industry partners to determine an appropriate dose level.

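### Phase I starts at its top dose level, but the written rules send a tolerated level 0 to a higher level that does not exist, and the MTD definition cannot name it

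*Combined protocol and SAP*

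**What the plan says.** The Phase I dose table in Section 7.41 is headed "Dose De-Escalation". It lists level 0 (45 mg twice daily), level -1 (30 mg) and level -2 (15 mg), and marks level 0 as the "starting dose level". Section 16.42 agrees: "The first cohort of three patients will be treated at dose level 0". Nothing is listed above level 0.

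For the favourable results, Section 16.422 states: "If DLT is not seen in any of the 3 patients, 3 new patients will be accrued and treated at the next higher dose level". Section 16.423 deals with one DLT in the first three; if a DLT "is not seen in any of the three additional patients, 3 new patients will be accrued and treated at the next higher dose level".

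Section 16.41 gives the definition: "MTD is defined as the dose level below the lowest dose that induces dose-limiting toxicity (DLT) in at least one-third of patients". It adds: "A total of 6 patients treated at the MTD will be sufficient to identify common toxicities at the MTD". Section 16.111 makes the MTD the Phase I primary endpoint. Section 7.412 refers the reader to Section 16.42 for enrolment decisions at each level.

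Sections 16.1 and 16.2 plan two dose levels, up to 6 patients at each, and 6 to 12 patients in all. For toxicity, the Phase I rule in Section 16.52 closes a level with two or more DLTs and moves accrual down. Section 7.41 says what happens after that: "If dose level -1 does not meet MTD determination, the study will be stopped and evaluated by the principal investigator".

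**The concern.** The decision rules read as those of an escalation study, while the dose table is that of a de-escalation study. The two collide in the outcome that the trial hopes for. If level 0 is tolerated, the only written action cannot be carried out. The definition of the primary endpoint also yields no answer, because no toxic level has been seen for the MTD to sit beneath.

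Two smaller points follow. The operating characteristics in Section 16.427 describe escalation, which cannot happen from level 0, so the plan nowhere states the chance that level 0 is accepted. In addition, Phase II uses two terms for the Phase I patients it brings in: Section 16.112 refers to the recommended dose for the response analysis, and the Phase II part of Section 16.52 refers to the MTD for the safety count. These mean the same thing only if a tolerated level 0 counts as the MTD.

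**Working it through.** **Step 1. Follow each possible result at level 0 through the text.**

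| Result at level 0 | Written action | Can it be done? |
|---|---|---|
| 0 of 3 DLTs | 16.422: three new patients one level up | No, there is no such level |
| 1 of 3, then 0 of 3 | 16.423: three new patients one level up | No, there is no such level |
| 1 of 3, then 1 or more of 3 | 16.423, 16.424: MTD exceeded; 16.52: accrue at the level below | Yes |
| 2 or 3 of 3 | 16.52: close the level and accrue at the level below | Yes |
| Level -1 also fails | 7.41: stop and evaluate | Yes |

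The gap is confined to the first two rows. Section 16.424 and the Phase I rule in Section 16.52 apply only once there are two or more DLTs, so neither fills it.

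**Step 2. Apply the definition in Section 16.41 to those two rows.** The MTD is the level beneath the lowest level with DLTs in at least one-third of patients. With 0 of 3, or 1 of 6, level 0 is below one-third. No toxic level exists, so no level satisfies the definition.

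**Step 3. Reproduce the table in Section 16.427.** Let p be the true DLT rate. The written escalation event is 0 of 3, or 1 of 3 followed by 0 of 3:

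P(escalate) = (1−p)³ + 3p(1−p)² × (1−p)³ = (1−p)³ + 3p(1−p)⁵.

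At p = 0.20 this is 0.512 + 0.197 = 0.709, printed as 0.71. All five rows reproduce. At level 0 these are also the probabilities of reaching the two rows that have no workable action.

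**Step 4. Compute acceptance under the inferred rule.** The inputs are six patients at the accepted dose (16.41, 16.2) and a DLT count below two in six (16.41, 16.424):

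P(accept) = (1−p)⁶ + 6p(1−p)⁵.

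At p = 0.20 this is 0.262 + 0.393 = 0.655.

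**Step 5. Explain the difference.** The rules part on one path only: 0 of 3, then two or more of the next three.

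Gap = (1−p)³ × [3p²(1−p) + p³]. At p = 0.20 this is 0.512 × 0.104 = 0.053.

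| True DLT rate | Printed in 16.427 | Reproduced | At most 1 DLT in 6 | Gap |
|---|---|---|---|---|
| 10% | 0.91 | 0.906 | 0.886 | 0.020 |
| 20% | 0.71 | 0.709 | 0.655 | 0.053 |
| 30% | 0.49 | 0.494 | 0.420 | 0.074 |
| 40% | 0.31 | 0.309 | 0.233 | 0.076 |
| 50% | 0.17 | 0.172 | 0.109 | 0.063 |

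**Step 6. Check the sample size under the inferred rule.** Acceptance of level 0 uses 6 evaluable patients. If level 0 closes after 3 or 6 patients, level -1 adds 3 or 6. The possible totals are 6, 9 or 12, inside the planned 6 to 12.

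**The case against.** The best reply is that this is template wording with a recoverable meaning. Six patients per level, two levels and six patients at the MTD all point to expanding level 0 and carrying it forward. The sentence in Section 7.41 about level -1 treats the MTD as something a level can itself meet. The Registration Office assigns the dose and the table lists nothing above 45 mg. All of this stands as evidence of intent. It does not remove the problem: after 0 of 3, expanding level 0 goes against the explicit instruction in Section 16.422, and Section 16.41 still needs a toxic level above. Describing the design as a standard 3+3 does not settle it either, because Section 16.42 writes out its own rules. The numbering passes from 16.424 to 16.426, but even a rule at 16.425 would leave 16.41, 16.422 and 16.423 needing change.

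Several stronger readings are tempting, and the documents do not support them:

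- **The Phase I rules can only escalate.** They cannot be read that way: Sections 16.422 to 16.424 also contain wording for moving down and for stopping, and Sections 16.52 and 7.41 complete the toxic branch.
- **The table in Section 16.427 is wrong.** It is correct for a generic escalation step and is labelled as such. It simply does not answer the question that matters at level 0.
- **The Phase II dose cannot be set, or patients may be overdosed.** Sections 16.1 and 16.112 speak of a recommended dose, so a dose can still be chosen, and no higher dose exists to give.
- **Phase I patients would drop out of the Phase II safety count.** Read very literally, the window of nine patients would close after 9 − 6 = 3 new patients if the six level-0 patients count, and after 9 if they do not. The evident meaning of Section 16.52 is the dose carried forward. Its Phase I rule also reviews related Grade 4 or higher events over all cycles, and the team may suspend accrual without a boundary being crossed.
- **Sections 13.7 and 16.426 conflict in a way that could change the DLT result materially.** Section 13.7 replaces patients who stop in Cycles 1 and 2 for reasons other than toxicity. It does not say that toxicity stops are kept. Section 16.426 is the specific rule for determining the MTD. Counting such a stop as a DLT is ruled out, because Sections 7.421 and 16.41 admit only Cycle 2 events that meet the DLT definition.

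**Conclusion.** The concern holds for the favourable branch. When level 0 is tolerated, the written action is impossible and the primary endpoint has no defined value. This is a stated rule that cannot be followed, not merely missing detail. By the plan's own figures, the branch is reached with probability 0.91 at a true DLT rate of 10% and 0.71 at 20%.

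The numerical effect is modest. If the inferred rule of at most one DLT in six is adopted, level 0 is accepted with probability 0.89, 0.66, 0.42, 0.23 and 0.11 at DLT rates of 10% to 50%, against 0.91, 0.71, 0.49, 0.31 and 0.17 printed for escalation. These figures assume independent patients with a common DLT rate and full replacement of uninformative patients. The rule itself is an inference from Sections 16.1, 16.2 and 16.41.

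Nothing here shows that a patient would be wrongly dosed or that Phase II could not start. The text should be corrected because the primary endpoint should not depend on inference. The wording of Section 13.7 is a minor clarification.

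**What to change.** Rewrite Sections 16.422 to 16.424 as a de-escalation rule:

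- Level 0, with 0 or 1 DLT in three: expand to six.
- At most 1 DLT in six: level 0 is the MTD and recommended Phase II dose.
- Two or more DLTs at any point: go to level -1 under the same rule.
- Two or more DLTs at level -1: stop, as Section 7.41 already provides.

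Amend Section 16.41 so that the MTD/recommended Phase II dose is the highest tested level with at most 1 DLT in six patients. Use that one term in Section 16.112 and in the Phase II part of Section 16.52, so that the response analysis and the safety count draw on Phase I patients from the same dose level.

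Replace the table in Section 16.427, or add a column to it, with the acceptance probabilities 0.89, 0.66, 0.42, 0.23 and 0.11. As a minor clarification, state that Section 16.426 governs the DLT denominator and word Section 13.7 to match.

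The cost is protocol wording and five recalculated numbers. No patients are added. The one drawback is that the stated probabilities become 0.02 to 0.08 less favourable.
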